#### 6.9.1. Rescue Medicine

There is no rescue therapy to reverse the AEs observed with PF-07081532; standard medical supportive care must be provided to manage the AEs, including administration of carbohydrates to treat HAEs (see Section 8.3.6).

## 6.9.2. Management of Nausea and Vomiting

Nausea and vomiting have been reported with administration of GLP-1R agonists and also with administration of PF-07081532. Study participants complaining of nausea may be managed conservatively with bed rest and/or fluid management at the discretion of the investigator. If nausea and vomiting are not amenable to conservative management, anti-emetics (eg, prochlorperazine, promethazine, ondansetron) may be administered at the investigator's discretion with notification to the sponsor and entry in the CRF.

## 7. DISCONTINUATION OF STUDY INTERVENTION AND PARTICIPANT DISCONTINUATION/WITHDRAWAL

#### 7.1. Discontinuation of Study Intervention

It may be necessary for a participant to permanently discontinue study intervention. Reasons for permanent discontinuation of study intervention include the following:

- Criteria for a potential Hy's law case are met (see Appendix 6).
- Intent to become pregnant or pregnancy confirmed by serum  $\beta$ -hCG testing.
- Safety or tolerability concern arises, in particular if not responsive to symptomatic management, dosing with study intervention may be stopped in an individual participant at investigator discretion.
- Based on mental health assessment as outlined in Section 8.3.8.3, should be discontinued from dosing at investigator discretion.
- If the criteria for permanent discontinuation are met, the site should notify the sponsor Medical Monitor or sponsor Clinician.
- Positive SARS-CoV-2 test (see Section 8.3.5).
- Potential or confirmed AKI (see Section 7.1.1).

Note that discontinuation of study intervention does not represent withdrawal from the study. If study intervention is permanently discontinued, the participant should remain in the study to be evaluated for an ET visit. See the SoA for data to be collected at the time of discontinuation of study intervention and follow-up for any further evaluations that need to be completed.

In the event of discontinuation of study intervention, it must be documented on the appropriate CRF/in the medical records whether the participant is discontinuing further receipt of study intervention or also from study procedures, post-treatment study follow-up, and/or future collection of additional information.

#### 7.1.1. Potential Cases of Acute Kidney Injury

Abnormal values in SCr concurrent with presence or absence of increase in BUN that meet the criteria below, in the absence of other causes of kidney injury, are considered potential cases of acute kidney injury and should be considered important medical events.

An increase of  $\geq$ 0.3 mg/dL (or  $\geq$ 26.5  $\mu$ mol/L) in SCr level relative to the participant's own baseline measurement should trigger another assessment of SCr as soon as practically feasible, preferably within 48 hours from awareness.

If the second assessment (after the first observations of  $\geq$ 0.3 mg/dL [or  $\geq$ 26.5  $\mu$ mol/L] in SCr relative to the participant's own baseline measurement) is  $\geq$ 0.4 mg/dL (or  $\geq$ 35.4  $\mu$ mol/L), the participant should be discontinued from the study and adequate, immediate, supportive measures taken to correct apparent acute kidney injury.

Participants should return to the investigator site and be evaluated as soon as possible, preferably within 48 hours from awareness of the second assessment confirming abnormal SCr result. This evaluation should include laboratory tests, detailed history, and physical assessment. In addition to repeating SCr, laboratory tests should include serum BUN, serum creatine kinase, and serum electrolytes (including at a minimum potassium, sodium, phosphate/phosphorus, and calcium), in addition to urinary dipstick, urine microscopic examination, and urinary indices. All cases confirmed on repeat testing as meeting the laboratory criteria for acute kidney injury, with no other cause(s) of laboratory abnormalities identified, should be considered potential cases of drug-induced kidney injury irrespective of availability of all the results of the investigations performed to determine etiology of the abnormal SCr. If  $\geq$ 2 healthy participants in a given treatment arm are noted to have 2 consecutive SCr results of  $\geq$ 0.3 mg/dL (or  $\geq$ 26.5 µmol/L), an assessment of whether the finding may be considered an adverse drug reaction should be undertaken.

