#### 8. STUDY ASSESSMENTS AND PROCEDURES

#### 8.1. Administrative Procedures

The investigator (or an appropriate delegate at the investigator site) must obtain a signed and dated ICD before performing any study-specific procedures.

Study procedures and their timing are summarized in the SoA. Protocol waivers or exemptions are not allowed.

Adherence to the study design requirements, including those specified in the SoA, is essential and required for study conduct.

All screening evaluations must be completed and reviewed to confirm that potential participants meet all eligibility criteria. The investigator will maintain a screening log to record details of all participants screened and to confirm eligibility or record reasons for screening failure, as applicable.

Safety issues should be discussed with the sponsor immediately upon occurrence or awareness to determine whether the participant should continue or discontinue study intervention.

Participants will be screened within 28 days prior to administration of the study intervention to confirm that they meet the study population criteria for the study.

Every effort should be made to ensure that protocol-required tests and procedures are completed as described. However, it is anticipated that from time to time there may be circumstances outside the control of the investigator that make it unfeasible to perform the test. In these cases, the investigator must take all steps necessary to ensure the safety and well-being of the participant. When a protocol-required test cannot be performed, the investigator will document the reason for the missed test and any corrective and preventive actions that they have taken to ensure that required processes are adhered to as soon as possible. The study team must be informed of these incidents in a timely manner.

If an IV catheter is utilized for blood sample collections, ECGs and vital sign assessments (pulse rate and BP) should be collected prior to the insertion of the catheter.

For samples being collected and shipped, detailed collection, processing, storage, and shipment instructions and contact information will be provided to the investigator site prior to initiation of the study.

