  - Preexisting AST or ALT baseline values above the normal range: AST or ALT values  $\geq 2$  times the baseline values AND  $\geq 3 \times \text{ULN}$ ; or  $\geq 8 \times \text{ULN}$  (whichever is smaller).
  - Preexisting values of T bili above the normal range: T bili level increased from baseline value by an amount of  $\ge 1 \times ULN$  or if the value reaches  $\ge 3 \times ULN$  (whichever is smaller).

Rises in AST/ALT and T bili separated by more than a few weeks should be assessed individually based on clinical judgment; any case where uncertainty remains as to whether it represents a potential Hy's law case should be reviewed with the sponsor.

The participant should return to the investigator site and be evaluated as soon as possible, preferably within 48 hours from awareness of the abnormal results. This evaluation should include laboratory tests, detailed history, and physical assessment.

In addition to repeating measurements of AST and ALT and T bili for suspected Hy's law cases, additional laboratory tests should include albumin, CK, direct and indirect bilirubin, GGT, PT/INR, total bile acids, and alkaline phosphatase. Consideration should also be given to drawing a separate tube of clotted blood and an anticoagulated tube of blood for further testing, as needed, for further contemporaneous analyses at the time of the recognized initial abnormalities to determine etiology. A detailed history, including relevant information, such as review of ethanol, acetaminophen/paracetamol (either by itself or as a coformulated product in prescription or over-the-counter medications), recreational drug, or supplement (herbal) use and consumption, family history, sexual history, travel history, history of contact with a jaundiced person, surgery, blood transfusion, history of liver or allergic disease, and potential occupational exposure to chemicals, should be collected. Further testing for acute hepatitis A, B, C, D, and E infection, liver imaging (eg, biliary tract), and collection of serum samples for acetaminophen/paracetamol drug and/or protein adduct levels may be warranted.

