# 10.7. Appendix 7: Kidney Safety: Monitoring Guidelines

# 10.7.1. Laboratory Assessment of Change in Kidney Function and Detection of Kidney Injury

Standard kidney safety monitoring requires assessment of baseline and postbaseline serum creatinine (Scr measurement to estimate glomerular filtration rate [Scr-based eGFR] or creatinine clearance [eCrCl]). Baseline and postbaseline serum Scys makes it feasible to distinguish AKI from other causes of Scr increase. If Scr increase is confirmed after baseline, then reflex measurement of Scys is indicated to estimate the combined Scr-Scys eGFR calculation (for adults only).

Regardless of whether kidney function monitoring tests are required as a routine safety monitoring procedure in the study, if the investigator or sponsor deems it necessary to further assess kidney safety and quantify kidney function, then these test results should be managed and followed per standard of care.

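### Protocol 7.1.1 words the creatinine stopping threshold as an absolute 0.4 mg/dL instead of an increase of 0.4 mg/dL from baseline (minor wording correction)

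*Protocol*

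**What the plan says.** Protocol Section 7.1 lists kidney injury among the reasons for permanent discontinuation of study intervention and defines it only by cross-reference: "Potential or confirmed AKI (see Section 7.1.1". The operative criteria are therefore those in Section 7.1.1, which sets three:

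- **First trigger.** An SCr increase of at least 0.3 mg/dL (26.5 µmol/L), "relative to the participant's own baseline measurement should trigger another assessment of SCr as soon as practically feasible". This is plainly a change from baseline.
- **Stopping criterion.** The sentence on the second assessment repeats the first trigger in brackets, closes the bracket and then gives the new threshold: "in SCr relative to the participant's own baseline measurement) is" at least 0.4 mg/dL (35.4 µmol/L). If it is met, "the participant should be discontinued from the study and adequate, immediate, supportive measures taken to correct apparent acute kidney injury".
- **Signal criterion.** If two or more healthy participants in an arm each have two consecutive SCr results of at least 0.3 mg/dL, "an assessment of whether the finding may be considered an adverse drug reaction should be undertaken". No baseline is mentioned here either.

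Appendix 7 (Section 10.7.1) says "If Scr increase is confirmed after baseline, then reflex measurement of Scys is indicated" but gives no 0.4 mg/dL criterion. The SAP has none.

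**The concern.** In the stopping sentence the words that make 0.3 mg/dL a change are inside the bracket about the first observation. Nothing attaches the idea of an increase, or of baseline, to the 0.4 mg/dL value, so grammatically it applies to the repeat creatinine itself.

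The repeat test exists to separate a rise that has resolved from one that persists. An absolute cut-off of 0.4 mg/dL cannot do that. A transient rise is a foreseeable event here: the risk table in Section 2.3.1 links renal impairment with this drug class mainly to nausea, vomiting and dehydration. A participant whose creatinine had recovered could be withdrawn, and the case carried forward as potential drug-induced kidney injury. Each needless stop would also remove later-period PK data from a study that enrols about 24 participants to obtain about 16 evaluable.

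**Working it through.** **Inputs.** The thresholds of 0.3 and 0.4 mg/dL come from Section 7.1.1. The documents give no baseline creatinine distribution, so baselines *b* of 0.5 to 1.2 mg/dL are assumed. The factor of 88.4 for converting mg/dL to µmol/L is the usual one for creatinine and is also not in the documents.

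**Step 1: the plan's own figures.** 0.3 × 88.4 = 26.5 and 0.4 × 88.4 = 35.4 µmol/L. Both stated conversions are right, so the fault lies only in the wording.

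**Step 2: the two readings.**

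- First trigger: value ≥ *b* + 0.3
- Intended stop: repeat ≥ *b* + 0.4
- Literal stop: repeat ≥ 0.4
- Gap between the stops: (*b* + 0.4) − 0.4 = *b*
- Fall below baseline needed to escape the literal stop: more than *b* − 0.4

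| Assumed baseline (mg/dL) | First trigger | Intended stop | Literal stop | Fall below baseline needed to escape |
|---|---|---|---|---|
| 0.5 | 0.8 | 0.9 | 0.4 | >0.1 (20%) |
| 0.7 | 1.0 | 1.1 | 0.4 | >0.3 (43%) |
| 0.9 | 1.2 | 1.3 | 0.4 | >0.5 (56%) |
| 1.2 | 1.5 | 1.6 | 0.4 | >0.8 (67%) |

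A repeat that has returned exactly to baseline meets the literal criterion in every row. The value that prompted the repeat already meets it for any baseline of 0.1 mg/dL or more, since 0.1 + 0.3 = 0.4. For comparison, the eGFR equations in Appendix 7 change form at creatinine values of 0.7 mg/dL (women) and 0.9 mg/dL (men), both well above 0.4.

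**Step 3: direction of the error.** For any *b* ≥ 0, a repeat at or above *b* + 0.4 is also at or above 0.4. The literal rule therefore captures every case the intended rule would, and misses none.

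**Step 4: opportunity.** In the protocol's Schedule of Activities (Tables 1 and 2), chemistry between the first PF-07081532 dose (Day 7) and the last (Day 52) is drawn on Period 3 Day 8 (Day 14), Period 6 Day 1 (Day 24) and Period 6 Day 20 (Day 43). That makes three scheduled draws during dosing. The documents give no rate of rises of 0.3 mg/dL or more, so no expected number of wrongful stops can be calculated.

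**The case against.** The best reply is that context settles the meaning. Section 7.1.1 opens by confining itself to abnormal creatinine values, the preceding sentence defines the measure as an increase from baseline, and the text that follows speaks of the second assessment confirming an abnormal result. Appendix 7 also speaks of a confirmed increase. The closing sentence uses the same shorthand with 0.3 mg/dL, which could not sensibly be absolute. Few investigators would withdraw someone whose creatinine had returned to normal, and Section 8.1 says safety issues should be discussed with the sponsor "to determine whether the participant should continue or discontinue study intervention". Participants who discontinue may be replaced (Section 4.1), and the SAP version history records that enough participants reached 240 mg QD.

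Most of this stands, and it is why the point is small. It does not make the wording right: no other text restates 0.4 mg/dL as a change, and Section 7.1 relies on 7.1.1 alone. Section 8.1 also allows no waivers, so a stopping threshold should not depend on the reader inferring its meaning. Appendix 6 shows that the baseline reference can be written into such a rule: "T bili level increased from baseline value by an amount of" a stated multiple of the upper limit of normal.

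A further objection is that the count of three draws covers dosing only. That is correct: Day 53, follow-up, early-termination and unscheduled samples add opportunities. The conclusion does not depend on the count.

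**Conclusion.** The concern holds. As written, the confirmation threshold in Section 7.1.1 is an absolute creatinine of 0.4 mg/dL, and the closing sentence has the same omission at 0.3 mg/dL, although that one only prompts an assessment. On assumed baselines of 0.5 to 1.2 mg/dL the literal stop lies 0.5 to 1.2 mg/dL below the intended one, so the repeat test loses its purpose.

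The practical weight is low. The intended meaning can be inferred, a first rise of at least 0.3 mg/dL is needed before the rule applies, and the error runs only toward over-stopping. No endpoint definition, analysis or sample-size calculation is affected. This is a minor wording correction that should be made because the sentence is an operative stopping rule.

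**What to change.** Make two changes in Protocol Section 7.1.1:

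1. Stopping criterion: *If the second assessment confirms an increase of ≥0.4 mg/dL (≥35.4 µmol/L) relative to the participant's own baseline measurement*, followed by the existing action.
2. Closing sentence: replace the reference to consecutive results with *2 consecutive SCr increases of ≥0.3 mg/dL (≥26.5 µmol/L) relative to the participant's own baseline*.

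The numerical thresholds stay as they are. The cost is two phrases in one section, with no change to visits, samples, participant status, analysis or sample size.

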## 7.1.2. Temporary Discontinuation

If participants are not able to tolerate titration to higher doses of PF-07081532 (eg,  $\geq$  200 mg QD) titration to the next dose level may be delayed temporarily, with *sponsor approval only*.

#### 7.2. Participant Discontinuation/Withdrawal From the Study

A participant may withdraw from the study at any time at their own request. Reasons for discontinuation from the study include the following:

- Refused further study procedures.
- Lost to follow-up.
- Death.
- Study terminated by sponsor.
- Safety or behavioral reasons at the discretion of the investigator, including reasons related to mental health assessments.
- Positive SARS-CoV-2 Test.

At the time of discontinuing from the study, if possible, an early discontinuation visit should be conducted. See the SoA for assessments to be collected at the time of study discontinuation and follow-up and for any further evaluations that need to be completed.

The early discontinuation visit applies only to participants who are enrolled/randomized and then are prematurely withdrawn from the study. Participants should be questioned regarding their reason for withdrawal.

If a participant withdraws from the study, they may request destruction of any remaining samples taken and not tested, and the investigator must document any such requests in the site study records and notify the sponsor accordingly.

If the participant withdraws from the study and also withdraws consent (see Section 7.2.1) for disclosure of future information, no further evaluations will be performed and no additional data will be collected. The sponsor may retain and continue to use any data collected before such withdrawal of consent.

#### 7.2.1. Withdrawal of Consent

Participants who request to discontinue receipt of study intervention will remain in the study and must continue to be followed for protocol-specified follow-up procedures. The only exception to this is when a participant specifically withdraws consent for any further contact with them or persons previously authorized by the participant to provide this information. Participants should notify the investigator in writing of the decision to withdraw consent from future follow-up, whenever possible. The withdrawal of consent should be explained in detail in the medical records by the investigator, as to whether the withdrawal is only from further receipt of study intervention or also from study procedures and/or posttreatment study follow-up, and entered on the appropriate CRF page. In the event that vital status (whether the participant is alive or dead) is being measured, publicly available information should be used to determine vital status only as appropriately directed in accordance with local law.

#### 7.3. Lost to Follow-up

A participant will be considered lost to follow-up if the participant repeatedly fails to return for scheduled visits and is unable to be contacted by the study site.

The following actions must be taken if a participant fails to attend a required study visit:

- The site must attempt to contact the participant and reschedule the missed visit as soon as possible. Counsel the participant on the importance of maintaining the assigned visit schedule and ascertain whether the participant wishes to and/or should continue in the study;
- Before a participant is deemed lost to follow-up, the investigator or designee must make every effort to regain contact with the participant (where possible, 3 telephone calls and, if necessary, a certified letter to the participant's last known mailing address or local equivalent methods). These contact attempts should be documented in the participant's medical record;
- Should the participant continue to be unreachable, the participant will be considered to have withdrawn from the study.

#### 8. STUDY ASSESSMENTS AND PROCEDURES

#### 8.1. Administrative Procedures

The investigator (or an appropriate delegate at the investigator site) must obtain a signed and dated ICD before performing any study-specific procedures.

Study procedures and their timing are summarized in the SoA. Protocol waivers or exemptions are not allowed.

Adherence to the study design requirements, including those specified in the SoA, is essential and required for study conduct.

All screening evaluations must be completed and reviewed to confirm that potential participants meet all eligibility criteria. The investigator will maintain a screening log to record details of all participants screened and to confirm eligibility or record reasons for screening failure, as applicable.

Safety issues should be discussed with the sponsor immediately upon occurrence or awareness to determine whether the participant should continue or discontinue study intervention.

Participants will be screened within 28 days prior to administration of the study intervention to confirm that they meet the study population criteria for the study.

Every effort should be made to ensure that protocol-required tests and procedures are completed as described. However, it is anticipated that from time to time there may be circumstances outside the control of the investigator that make it unfeasible to perform the test. In these cases, the investigator must take all steps necessary to ensure the safety and well-being of the participant. When a protocol-required test cannot be performed, the investigator will document the reason for the missed test and any corrective and preventive actions that they have taken to ensure that required processes are adhered to as soon as possible. The study team must be informed of these incidents in a timely manner.

If an IV catheter is utilized for blood sample collections, ECGs and vital sign assessments (pulse rate and BP) should be collected prior to the insertion of the catheter.

For samples being collected and shipped, detailed collection, processing, storage, and shipment instructions and contact information will be provided to the investigator site prior to initiation of the study.

The total blood sampling volume for individual participants in this study is approximately 535 mL. The actual collection times of blood sampling may change. Additional blood samples may be taken for safety assessments at times specified by Pfizer, provided the total volume taken during the study does not exceed 550 mL during any period of 56 consecutive days.

To prepare for study participation, participants will be instructed on the information in the Lifestyle Considerations and Concomitant Therapy sections of the protocol.

## 8.2. Efficacy Assessments

Not applicable.

